4.2 Strategies for Recruitment and Retention

Both men and women of all races and ethnic groups are eligible for this trial. Subjects will be recruited at Sylvester Comprehensive Cancer Center (SCCC) via clinical practice offices.

5 TREATMENT PLAN

5.1 Method of Treatment Assignment

All patients will be treated on this single arm, open label, investigator-initiated Phase 2 study with an investigational treatment of nivolumab in combination with relatlimab until disease progression or intolerable toxicity for up to 24 months.

5.2 Dosing and Administration

Enrolled patients will be treated in the outpatient setting. Nivolumab 480 mg will be mixed in the same bag with Relatlimab 160 mg and will be administered intravenously over 60 minutes (+ or –5 minutes) every 4 weeks. Each cycle will be approximately 4 weeks in length. Both drugs will be administered until disease progression or intolerable toxicity for up to 24 months.

Table 2. **Dosing and Administration Schedule Nivolumab + Relatlimab Combination Treatment (All cycles)**

Drug	Dose	Day 1 (+/- 3 days)	Day 28 (+/- 3 days)
Nivolumab	480 mg	X	X
Relatlimab	160 mg	X	X

5.3 Missed doses

Patients who miss a nivolumab plus relatlimab dose at the usual required time should skip additional therapy until the next cycle.

5.4 Concomitant Therapy

Nivolumab and relatlimab will be administered concomitantly every 4 weeks (qw4) until disease progression or intolerable toxicity for up to 24 months. For this protocol, a prescription medication is defined as a medication that can be prescribed only by a properly authorized/licensed clinician. Medications to be reported in the Case Report Form (CRF) are concomitant prescription medications, over-the-counter medications and supplements.

5.5 Premedication

No premedication is recommended or required.

5.6 Prohibited Therapies

Subjects are prohibited from receiving the following therapies during the Screening and Treatment Phase (including retreatment for post-complete response relapse) of this trial:

- Antineoplastic systemic chemotherapy or biological therapy
- Immunotherapy not specified in this protocol

- Chemotherapy
- Investigational agents other than nivolumab and relatlimab
- Live vaccines within 30 days prior to the first dose of trial treatment and while participating in the trial. Examples of live vaccines include, but are not limited to, the following: measles, mumps, rubella, varicella/zoster, yellow fever, rabies, BCG, and typhoid vaccine.
- Radiation therapy
 - Note: Palliative radiation therapy or treatment to a symptomatic solitary lesion or to the brain may be allowed at the investigator's discretion as previously described
- Systemic glucocorticoids for any purpose other than to modulate symptoms from an event of clinical interest of suspected immunologic etiology. The use of physiologic/replacement doses of corticosteroids is allowed.
- Subjects who, in the assessment by the investigator, require the use of any of the aforementioned treatments for clinical management should be removed from the trial. Subjects may receive other medications that the investigator deems to be medically necessary.

5.7 Study Intervention Compliance

All doses of study treatments (nivolumab and relatlimab) will be administered at the investigational site by designated medical staff.

The information related to each trial drug administration, including the date, time, and dose of study drug, will be recorded on Velos. The Investigator will make sure that the information entered into the CRF regarding drug administration is accurate for each patient. Any reason for noncompliance should be documented.

Noncompliance is defined as a patient missing 2 doses of nivolumab plus relatlimab for non-medical reasons. If ≥ 2 doses of the study drug treatment are missed and the interval between the subsequent dose and the last administered treatment is longer than 6 weeks for nonmedical reasons, the criteria of insufficient compliance will have been met as well.

Non-compliant patient slots can be replaced by a new eligible patient.

5.8 Contraception

Contraception Requirements for Women:

The study drug may be absorbed into bodily secretions such as vaginal fluids and then passed on to the female participant's partner during sex. Male sexual partners must wear a condom to avoid being exposed to the study drug.

The study drug may harm a fetus or a breastfeeding baby.

If a woman is pregnant or breastfeeding, she cannot take part in this study.

If woman thinks she may be pregnant, she should not volunteer for this study.

Women of childbearing potential must have a pregnancy test before beginning the study and while in the study.

Women of childbearing potential must not get pregnant or breastfeed while in this study and for at least 24 weeks after the last dose of the study drug. Women must not donate an egg for at least 5 months after the last dose of study medication.

Women of childbearing potential must take measures to avoid becoming pregnant while in this study.

The following are acceptable measures of contraception:

- Abstinence (not having sexual relations with a person of the opposite sex)
- Implantable hormone (e.g. Norplant)
- Intrauterine Device (IUD)
- Male partner has had a vasectomy
- Female sterilization
- Hormonal injection
- Oral contraceptives

Participants must use contraception, at least starting at screening before starting study treatment unless they abstain from sexual intercourse. Participants must use contraception during study treatment and for at least 24 weeks after stopping study treatment.

Contraception Requirements for Men

Study drug may be absorbed into bodily secretions such as semen and then passed on to partners during sex. Participants must wear a condom to avoid being exposed to the study drug.

There may be risks to the embryo/fetus if female sexual partner is pregnant or becomes pregnant while the participant in this study. If the participant's partner is a woman of child bearing potential, the participant and their partner must either practice total abstinence or use effective contraception while participating in this study. One of the following forms of contraception should be used by the participant and their partner:

- Abstinence (not having sexual relations with a person of the opposite sex)
- Implantable hormone (e.g. Norplant)
- Intrauterine Device (IUD)
- Vasectomy
- Female sterilization
- Hormonal injection
- Oral contraceptives

Participants must use contraception during study treatment and for at least 7 months after stopping study treatment. Participants should also refrain from donating semen during therapy and for 24 weeks after stopping the therapy.

There is theoretical concern that study treatment can result in sperm abnormalities and/or can transmit harmful substances in their semen during sex. Therefore, males must remain abstinent or use a condom, even if they have undergone a vasectomy.

If a participant's female partner becomes pregnant or suspects becoming pregnant during study treatment or within 24 weeks after completing study treatment, the participant must inform the Study Doctor immediately. The Study Doctor may want to follow the pregnancy and may ask the female partner to sign a consent form so they can collect information about the outcome of the pregnancy.

5.9 Breast Feeding

Participants must not breast-feed while receiving study treatment and for 24 weeks following the last dose of study treatment.

5.10 Blood Donation

Participants must not donate blood during the study or for 12 weeks after the last dose of protocol therapy.

5.11 Duration of Follow Up

All study subjects will be followed as per standard of care for tumor recurrence. Following the completion of the combination nivolumab and relatlimab therapy, patients will be followed for 2 years to obtain information on disease progression and overall survival.

5.12 End of Study Definition

A study participant is considered to have completed the study once he or she completes all phases of the study treatment and study related laboratory tests. The primary and secondary clinical aims endpoints will be available for analysis once all patients have been followed for 2 years after completing the nivolumab and relatlimab combination therapy. Therefore, the clinical trial will be considered completed when the last participant has completed all phases of the study including the last visit or the last scheduled procedure shown in the Schedule of Activities (SoA), and the clinical endpoints are available for analysis.

6 STUDY INTERVENTION DISCONTINUATION AND PARTICIPANT DISCONTINUATION/WITHDRAWAL

6.1 Discontinuation of Study Intervention

Discontinuation from nivolumab plus relatlimab does not mean discontinuation from the study, and remaining study procedures should be completed as indicated by the protocol. Patients who received at least 2 doses of the combination treatment will be considered evaluable and the remaining study procedures should be completed as indicated by the protocol in Section 6.2.

If a clinically significant finding is identified (including, but not limited to changes from baseline) after enrollment, the Investigator or qualified designee will determine if any change in participant management is needed. Any new clinically relevant finding will be reported as an adverse event (AE).

The data to be collected at the time of study intervention discontinuation will include the following:

- Progression Free Survival
- Overall Survival
- Adverse events

6.2 Participants Taken Off Study

Patients who are enrolled but do not receive at least one dose of nivolumab or relatlimab because of noncompliance or clinical reasons will be taken off study and will receive standard treatment. These patients will not be included in the efficacy analysis and will be replaced.

6.3 Participant Discontinuation/Withdrawal from the Study

Participants are free to withdraw from participation in the study at any time upon request. An Investigator may discontinue or withdraw a participant from the study for the following reasons:

- Pregnancy
- Significant study intervention non-compliance
- Lost-to-follow up; unable to contact subject
- Any event or medical condition or situation occurs such that continued collection of follow-up study data would not be in the best interest of the participant or might require an additional treatment that would confound the interpretation of the study
- Disease progression which requires discontinuation of the study intervention
- Participant meets an exclusion criterion (either newly developed or not previously recognized) that precludes further study participation
- Participant unable to receive nivolumab and relatlimab combination treatment for 2 cycles over a period of 12 weeks.

The reason for participant discontinuation or withdrawal from the study will be recorded on the Case Report Form (CRF).

6.3.1 Data Retention When Subjects Withdraw from FDA-Regulated Clinical Trials

An investigator may ask a subject who is withdrawing whether the subject wishes to provide continued follow-up and further data collection subsequent to their withdrawal from the interventional portion of the study. Under this circumstance, the discussion with the subject would distinguish between study-related interventions and continued follow-up of associated clinical outcome information, such as medical course or laboratory results obtained through non-invasive chart review, and address the maintenance of privacy and confidentiality of the subject's information.

If a subject withdraws from the interventional portion of the study, but agrees to continued follow-up of associated clinical outcome information as described in the previous bullet, the investigator must obtain the subject's informed consent for this limited participation in the study (assuming such a situation was not described in the original informed consent form). In accordance with FDA regulations, IRB approval of informed consent documents would be required (21 CFR 50.25, 56.109(b), 312.60, 312.66, 812.100).

6.4 Participant Replacement Criteria

Subjects who sign the informed consent form and do not receive the study intervention may be replaced. Subjects who sign the informed consent, receive the study intervention, and subsequently withdraw, or are withdrawn or discontinued from the study due to non-compliance will be replaced by a new eligible patient.

6.5 Lost to follow up

A participant will be considered lost to follow-up if he or she fails to return for two scheduled treatment cycles over a period of 12 weeks and is unable to be contacted by the study site staff.

The following actions must be taken if a participant fails to return to the clinic for a required study visit:

- The site will attempt to contact the participant and reschedule the missed visit 3 times and counsel the participant on the importance of maintaining the assigned visit schedule and ascertain if the participant wishes to and/or should continue in the study.
- Before a participant is deemed lost to follow-up, the Investigator or designee will make every effort to regain contact with the participant (where possible, 3 telephone calls and, if necessary, a certified letter to the participant's last known mailing address or local equivalent methods). These contact attempts should be documented in the participant's medical record or study file.
- Should the participant continue to be unreachable, he or she will be considered to have withdrawn from the study with a primary reason of lost to follow-up.

7 TREATMENT DISCONTINUATION AND ADVERSE EVENT MANAGEMENT

Dose reductions or dose escalations are not permitted in this study. Dose delay criteria as noted below apply for all drug-related adverse events regardless of whether or not the event is attributed to nivolumab, relatlimab, or both. All study drugs must be delayed until treatment can resume. Reasons for permanent treatment discontinuation include the following:

- Any drug-related/immune-related Grade 4 toxicity, except for endocrinopathy and asymptomatic elevations of amylase and lipase.
- Any Grade 3 elevation of liver function tests or colitis not responding to steroids, infliximab and/or mycophenolate mofetil.
- Any other drug-related/immune-related Grade 3 toxicity, **EXCLUDING:**
 - *Grade 3 nausea/vomiting controlled by medical intervention within 72 hours*
 - *Grade 3 immune-related AEs (other than ocular events, colitis, myocarditis and pneumonitis) that improve to Grade \leq 1 or baseline within 14 days after the initiation of supportive care or corticosteroid therapy*
 - *Grade 3 endocrinopathy that is managed with or without systemic corticosteroid therapy and/or hormone replacement therapy and the subject is asymptomatic or minimally or transiently symptomatic based on Investigator assessment*
 - *Grade 3 fatigue lasting \leq 7 days from onset*
 - *Grade 3 rash in the absence of desquamation, with no mucosal involvement, that does not require systemic steroids, that does not interfere with activities of daily living and resolves to Grade 1 by the next dose of scheduled treatment or 14 days, whichever is longer*
 - *Any grade vitiligo or alopecia*
- Grade 2 or higher episcleritis, uveitis, or iritis
- Grade 2 pneumonitis that does not resolve to \leq Grade 1 within 3 days of initiation of maximal supportive treatment.

If treatment is withheld > 6 weeks from the last dose, the participant must be permanently discontinued from study therapy.

Table 3. Adverse Event Management Rules

Toxicity	Hold Treatment For Grade	Timing for Restarting Treatment	Treatment Discontinuation
Diarrhea/Colitis	2-3	Toxicity resolves to Grade 0-1	Toxicity does not resolve within 6 weeks of last dose or inability to reduce corticosteroid to 10 mg or less of prednisone or equivalent per day within 12 weeks
	4	Permanently discontinue	Permanently discontinue
AST, ALT, or Increased Bilirubin	2	Toxicity resolves to Grade 0-1	Toxicity does not resolve within 6 weeks of last dose
	3-4	Permanently discontinue (see exception below) ^a	Permanently discontinue
Type 1 diabetes mellitus (if new onset) or Hyperglycemia	T1DM or 3-4	Hold therapy for new onset Type 1 diabetes mellitus or Grade 3-4 hyperglycemia associated with evidence of beta cell failure	Resume therapy when patients are clinically and metabolically stable
Hypophysitis	2-4	Toxicity resolves to Grade 0-1. Therapy can be continued while endocrine replacement therapy is instituted	Toxicity does not resolve within 6 weeks of last dose or inability to reduce corticosteroid to 10 mg or less of prednisone or equivalent per day within 6 weeks
Hyperthyroidism	3	Toxicity resolves to Grade 0-1	Toxicity does not resolve within 6 weeks of last dose or inability to reduce corticosteroid to 10 mg or less of prednisone or equivalent per day within 6 weeks
	4	Permanently discontinue	Permanently discontinue
Hypothyroidism		Therapy can be continued while thyroid replacement therapy is instituted	Therapy with can be continued while thyroid replacement therapy is instituted
Infusion Reaction	2 ^b	Toxicity resolves to Grade 0-1	Permanently discontinue if toxicity develops despite adequate premedication
	3-4	Permanently discontinue	Permanently discontinue
Pneumonitis	2	Toxicity resolves to Grade 0-1	Toxicity does not resolve within 6 weeks of last dose or inability to reduce corticosteroid to 10 mg or less of prednisone or equivalent per day within 6 weeks
	3-4	Permanently discontinue	Permanently discontinue
Renal Failure or Nephritis	2	Toxicity resolves to Grade 0-1	Toxicity does not resolve within 6 weeks of last dose or inability to reduce corticosteroid to 10 mg or less of prednisone or equivalent per day within 6 weeks
	3-4	Permanently discontinue	Permanently discontinue
All Other Drug-Related Toxicity ^c	3 or Severe	Toxicity resolves to Grade 0-1	Toxicity does not resolve within 6 weeks of last dose or inability to reduce corticosteroid to 10 mg or less of prednisone or equivalent per day within 6 weeks
	4	Permanently discontinue	Permanently discontinue

Note: Permanently discontinue for any severe or Grade 3 drug-related AE that recurs or any life-threatening event.

^a For patients with liver metastasis who begin treatment with Grade 2 AST or ALT, if AST or ALT increases by greater than or equal to 50% relative to baseline and lasts for at least 1 week then patients should be discontinued.

^b If symptoms resolve within one hour of stopping drug infusion, the infusion may be restarted at 50% of the original infusion rate (e.g., from 100 mL/hr to 50 mL/hr). Otherwise dosing will be held until symptoms resolve and the subject should be premedicated for the next scheduled dose.

^c Patients with intolerable or persistent Grade 2 drug-related AE may hold study medication at physician discretion. Permanently discontinue study drug for persistent Grade 2 adverse reactions for which treatment with study drug has been held, that do not recover to Grade 0-1 within 6 weeks of the last dose.

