1.8 Risk/Benefit Assessment

1.8.1 Nivolumab Known Potential Risks

The potential risks from treatment with nivolumab are described in detail in section 7.1 of the investigator's brochure. These include the following adverse events: pulmonary, gastrointestinal, hepatic, endocrinopathies, dermatologic, renal, neurologic, infusion reactions, lipase/amylase elevations, uveitis and visual complaints, and other immune-mediated adverse events such as myotoxicity (myositis, myocarditis, and rhabdomyolysis), solid organ and tissue transplant rejection, rapid-onset and severe graft-versus-host-disease GVHD, and complications of allogeneic hematopoietic stem cell transplantation (HSCT).

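### For certain endocrinopathies and asymptomatic amylase/lipase rises, the Section 7 list stops treatment at Grade 3 but exempts Grade 4, and Table 3 gives conflicting instructions at both grades

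*Combined protocol and SAP*

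**What the plan says.** Section 7 first gives a bulleted list of reasons for permanent discontinuation, then Table 3 with a Note beneath it.

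- **First bullet (Grade 4).** A reason to stop is "Any drug-related/immune-related Grade 4 toxicity, except for endocrinopathy and asymptomatic elevations of amylase and lipase". Neither exemption is limited by symptoms or duration.
- **Third bullet (Grade 3).** A reason to stop is "Any other drug-related/immune-related Grade 3 toxicity", followed by a set of exclusions. Two matter here. The general one covers Grade 3 immune-related events, apart from four named kinds, that return to Grade 1 or lower "or baseline within 14 days after the initiation of supportive care or corticosteroid therapy". The endocrine one applies where "the subject is asymptomatic or minimally or transiently symptomatic based on Investigator assessment". Amylase and lipase are not named in any Grade 3 exclusion.
- **Six-week rule.** "If treatment is withheld > 6 weeks from the last dose, the participant must be permanently discontinued from study therapy". It depends on the length of the hold, not on the grade.
- **Table 3.** Hyperthyroidism is held at Grade 3, with restart once it falls to Grade 0-1, and permanently stopped at Grade 4. The catch-all row for related toxicities without their own row does the same. Amylase and lipase have no row of their own.
- **Note under Table 3.** "Permanently discontinue for any severe or Grade 3 drug-related AE that recurs or any life-threatening event".

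**The concern.** A discontinuation list would be expected to give one readable instruction per event and grade. Here the two bullets were given different exceptions for the same two events, and the Grade 3 exceptions are the narrower ones. Read literally, some patients with the lesser grade must stop while the list exempts patients with the greater grade.

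The events are of a kind the protocol anticipates. Section 1.8.1 names "infusion reactions, lipase/amylase elevations, uveitis and visual complaints" among the nivolumab risks. Section 1.8.4 puts hypothyroidism and hyperthyroidism among the most frequent related events. Amylase and lipase are measured at every treatment cycle (10.2, 10.3, 10.8). Section 7 forbids dose reduction, so holding and stopping are the only dose-management tools.

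What is at stake is first the consistent, safe handling of individual patients. Where two mandatory instructions disagree, either course departs from one of them. That also leaves unclear how such a patient should be classified for the per-protocol set in 16.3, which excludes major protocol violations.

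**Working it through.** The plan states no figure on this point, so there is nothing to recompute. The check traces each event through the list and through Table 3 at Grade 3 and Grade 4.

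**Which exclusions can apply at Grade 3.** The general 14-day exclusion is withheld only from ocular events, colitis, myocarditis and pneumonitis. An immune-related amylase/lipase rise and an immune-related endocrinopathy can therefore both use it. Endocrinopathy also has its own symptom-based exclusion. The remaining exclusions (nausea/vomiting, fatigue, rash, vitiligo or alopecia) are irrelevant here.

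| Event | List, Grade 3 | List, Grade 4 | Table 3, Grade 3 | Table 3, Grade 4 |
|---|---|---|---|---|
| Asymptomatic amylase/lipase rise, immune-related, improved within 14 days | excluded | exempt | hold, may restart | stop |
| Asymptomatic amylase/lipase rise, not classed as immune-related or not improved within 14 days | **stop** | **exempt** | hold, may restart | stop |
| Hyperthyroidism meeting either exclusion | excluded | exempt | hold, may restart | stop |
| Hyperthyroidism meeting neither exclusion | **stop** | **exempt** | hold, may restart | stop |
| Hypophysitis, new type 1 diabetes or hyperglycemia, hypothyroidism, meeting neither exclusion | **stop** | **exempt** | no stop on grade alone | same as Grade 3 |

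The list columns describe the bullets only. The six-week rule can end treatment in any row.

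**Step 1, within the list.** Rows 2, 4 and 5 show the inversion: stop at Grade 3, exempt at Grade 4. Rows 1 and 3 do not. The inversion is real but confined to Grade 3 events that fall outside every exclusion.

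**Step 2, list against table.** In rows 2 and 4 the table disagrees with the list at both grades: the list stops at Grade 3 where the table holds, and exempts at Grade 4 where the table stops. In rows 1 and 3 they still disagree at Grade 4. In row 5 they disagree at Grade 3 only.

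**Step 3, the Note.** It stops treatment for a life-threatening event and makes no exception for endocrinopathy. For a Grade 4 endocrinopathy judged life-threatening, this contradicts the first bullet's exemption.

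**Step 4, precedence.** Section 7 does not say whether the list or the table governs.

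**A practical point on the 14-day exclusion.** Its clock runs from the start of supportive care or steroids, and an asymptomatic laboratory rise may prompt neither. Scheduled amylase/lipase tests are four weeks apart, and footnote 3 of the study calendar (10.8) ties extra tests to signs and symptoms. An investigator may order an earlier repeat, but the schedule does not provide one within 14 days.

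**The case against.** The strongest reply is that the problem is narrow and that the rest of Section 7 already prevents the worrying outcome. A Grade 3 endocrinopathy has two routes out of the third bullet, and must fail both before the list stops treatment. At Grade 4, Table 3 permanently stops hyperthyroidism and anything in the catch-all row, the Note stops life-threatening events, and the six-week rule ends any long hold. The list is also introduced as non-exhaustive, so being exempt from one bullet is not permission to continue. Finally, Sections 1.8.1 and 1.8.4 name the events without grade or duration, so they say little about how often the narrow cases would occur.

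Most of this stands, and it limits the point. A reader might infer that every symptomatic Grade 3 endocrinopathy ends treatment. The documents do not support that, because the general 14-day exclusion also covers endocrinopathy. A reader might also infer that Grade 4 patients simply continue under the protocol. That is true of the bullet alone, not of Section 7 as a whole.

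The reply does not remove the defect. Table 3 does not supply the missing consistency: it contradicts the first bullet at Grade 4 and, in the inverted cases, the third bullet at Grade 3. With no precedence stated, the investigator has conflicting instructions.

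**Conclusion.** The point holds in a limited form. Within the list, Grade 3 is stopped and Grade 4 exempted in two situations:

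- an asymptomatic amylase/lipase rise that is not classed as immune-related or does not improve to Grade 1 or lower, or baseline, within 14 days;
- an endocrinopathy whose symptoms exceed what its exclusion allows and that also does not improve to that level within 14 days.

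Table 3 and its Note conflict with the list and do not settle which applies. This rests on two readings: that amylase/lipase falls in the catch-all row, since it has no other, and that list and table have equal standing, since nothing says otherwise.

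No numerical size is claimed. A reader might want to compute the chance that at least one of 27 patients is affected. That needs the rate of Grade 3 events that fail every exclusion, which the documents do not give; a rate for all Grade 3-4 events would not serve. A reader might also count each stopped patient as 1/27 = 3.7 points of ORR. That assumes the patient would certainly have responded. At the design's 20% response rate the expected loss is at most 0.20 × 1/27 = 0.74 points, even if stopping removed all chance of response. Section 6.1 keeps patients with at least two doses evaluable after discontinuation, so a response is not necessarily lost.

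**What to change.** Reconcile five pieces of text: the first and third bullets of the Section 7 list, the Table 3 rows for hyperthyroidism and for all other related toxicity, and the Note under Table 3. After the change, endocrinopathy and asymptomatic amylase/lipase elevation should each have one consistent instruction at Grade 3 and one at Grade 4, the same wherever it appears. When the third bullet is revised, check the other endocrine rows of Table 3 against it. Amending the list alone would leave the conflicting table rows in place.

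Which instruction applies at each grade is a clinical decision for the sponsor-investigator's team; this review proposes none.

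The cost is a wording change in a protocol amendment, with no added data, visits or patients.

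### Section 7's bulleted list and Table 3 give different rules for permanent discontinuation, and no sentence says which governs

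*Combined protocol and SAP*

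**What the plan says.** Section 7 contains two texts that decide when treatment ends for good.

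**The list.** It opens with "Reasons for permanent treatment discontinuation include the following". Its relevant entries are:
- "Any drug-related/immune-related Grade 4 toxicity, except for endocrinopathy and asymptomatic elevations of amylase and lipase".
- Other Grade 3 drug-related or immune-related toxicity, subject to exclusions. One exclusion covers "Grade 3 immune-related AEs (other than ocular events, colitis, myocarditis and pneumonitis) that improve to Grade" 1 or lower, or to baseline, within 14 days of starting supportive care or steroids. Another covers fatigue of 7 days or less.
- "Grade 2 or higher episcleritis, uveitis, or iritis".
- Grade 2 pneumonitis not down to Grade 1 or lower "within 3 days of initiation of maximal supportive treatment".
- A bullet on Grade 3 liver tests and colitis, with a qualifier about non-response to immunosuppression.

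**Table 3.** It has its own restart and discontinuation columns. For Grade 2 pneumonitis, treatment is held and may restart at Grade 0-1. It ends if "Toxicity does not resolve within 6 weeks of last dose", or if the steroid dose cannot be brought to 10 mg or less of prednisone or equivalent per day within 6 weeks. Events without a row of their own fall under "All Other Drug-Related Toxicity". There, Grade 3 carries the same restart and stop criteria and Grade 4 ends treatment. Footnote c to that row adds: "Patients with intolerable or persistent Grade 2 drug-related AE may hold study medication at physician discretion".

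**The concern.** Where the list stops and the table permits restart, two investigators following the same protocol could treat the same patient differently, and one of them would re-dose a patient whom the other text removes from treatment.

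The events involved matter for this combination. Section 1.8.4 names myocarditis among the combination risks. It also places one Grade 4 myocarditis and one Grade 3 pneumonitis among the exceptions to drug-related events being reversible or manageable. Section 4.1 excludes patients with a history of myocarditis and screens on troponin. Section 13.9 lists myocarditis and uveitis as events of special interest. That section sets the order of output tables, so it does not by itself require a management row, but it shows that these events are expected to be watched.

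**Working it through.** No arithmetic decides this point. Each event and grade in the list was matched to its Table 3 row, or to the catch-all row if it has none, and the two actions were compared.

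*List stops, Table 3 allows restart*

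| Event | List | Table 3 | Route in Table 3 |
|---|---|---|---|
| Grade 2 pneumonitis | Stop if not Grade 1 or lower in 3 days of maximal supportive treatment | Restart at Grade 0-1; stop if unresolved by 6 weeks from last dose, or steroid not tapered in 6 weeks | Own row |
| Grade 3 myocarditis | Stop even if it recovers (carved out of the 14-day exclusion) | Hold; restart at Grade 0-1 | Catch-all |
| Uveitis, episcleritis, iritis | Stop from Grade 2 | Grade 2: hold is discretionary; Grade 3: hold and restart at Grade 0-1 | Footnote c, catch-all |
| Other Grade 3 events outside the exclusions (for example fatigue beyond 7 days, not otherwise excluded) | Stop | Hold; restart at Grade 0-1 within the 6-week criteria | Catch-all |

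*List exempts, Table 3 stops*

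| Event | List | Table 3 | Route in Table 3 |
|---|---|---|---|
| Grade 4 hyperthyroidism | Exempt as endocrinopathy | Stop | Own row |
| Immune-related Grade 3 nephritis improving within 14 days | Excluded | Stop | Own row |
| Grade 4 asymptomatic amylase or lipase | Exempt | Stop | Catch-all |

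**Dependent on parsing.** If the non-response qualifier covers liver tests as well as colitis, the list does not stop a steroid-responsive Grade 3 liver event. Table 3 stops at Grade 3-4, subject to footnote a. If the qualifier covers colitis only, there is no such difference.

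**Count.** Four entries in the first group (three named events and one class) and three in the second, so seven, plus one that depends on parsing. Of the seven, three meet a dedicated Table 3 row (Grade 2 pneumonitis, Grade 4 hyperthyroidism, Grade 3 nephritis) and four arise through the catch-all row.

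**Search for a ranking sentence.** None was found.
- The opening sentence on dose delay concerns attribution to one drug or the other.
- The general limit of 6 weeks from last dose agrees with Table 3 and ranks nothing.
- The note under Table 3 covers recurrent severe or Grade 3 events and life-threatening events, so it does not settle a first Grade 3 myocarditis.
- Reading the list as governing stopping and the table as governing holding fails, because Table 3 has a discontinuation column.

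**Checked and not counted.** Grade 3-4 pneumonitis and Grade 3-4 infusion reactions stop under both texts. Grade 4 hypophysitis and Grade 4 hyperglycemia stop automatically under neither. Grade 3 colitis uses different criteria in the two texts without a plain contradiction.

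**Hypothetical case.** Grade 2 pneumonitis is put on maximal supportive treatment on day 7 after a dose, is still Grade 2 on day 10 (7 + 3), and is resolved by day 20. The list stops the patient at day 10. Under Table 3 the patient can be dosed on schedule at day 28, provided the steroid criterion is met.

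**The case against.** **Specific over general.** The list deals expressly with Grade 3 myocarditis, the ocular inflammations and asymptomatic amylase or lipase, and a catch-all row would not ordinarily displace a specific line. This has force. A reader might infer that the protocol sanctions re-dosing after Grade 3 myocarditis; it does not, because the list says stop. What stands is that Table 3 is the working management table, sends that event to a row with a restart instruction, and carries no pointer back to the list. Grade 2 pneumonitis does not depend on this argument, since it has its own row.

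**Additive reading.** The list is introduced as non-exhaustive, so either text might suffice to stop. An exemption also limits its own bullet and does not instruct anyone to continue. This is why the second group is softer. The endocrinopathy exemption would still have effect for Grade 4 hypophysitis and hyperglycemia; only the amylase and lipase exemption would be emptied. But the additive rule is nowhere stated, and it would override Table 3's restart instruction for the first group.

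**Duration.** A reader might try to express the pneumonitis gap as a number of days on which the texts differ about a dose. The documents do not support one. It would need an assumed day on which supportive care starts, and it would depend on whether the skip-to-next-cycle rule in Section 5.3 applies to toxicity holds. If it does, a dose not given by day 31 (28 + 3) waits until about day 56 (2 x 28), beyond the 6-week limit of day 42.

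**Conclusion.** The inconsistency is real and should be corrected. The weight rests on the four entries where the list stops and Table 3 allows restart. Grade 2 pneumonitis is the firmest, because each text addresses it directly; myocarditis, ocular inflammation and the other Grade 3 events arise through the catch-all row and footnote c. The three exemption mismatches are secondary, and liver tests count only on one reading of their bullet.

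It would go too far to call all of these flat contradictions: most of the first group needs the catch-all row, and the second group could be reconciled by an additive reading. Nor do the documents support a claim about the primary result. The conflict concerns exposure and patient safety; the Simon design and its error rates do not depend on it. The conclusion assumes only that events without a row fall under the catch-all row, as its label indicates.

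**What to change.** Amend Section 7 as follows:
- State that treatment stops permanently if either the list or Table 3 requires it.
- Put the 3-day limit into the Grade 2 pneumonitis row, keeping the 6-week resolution and steroid-taper criteria.
- Add Table 3 rows for myocarditis (stop at Grade 3-4) and for uveitis, episcleritis and iritis (stop at Grade 2 or higher).
- Make the catch-all Grade 3 row allow restart only for events within the Section 7 exclusions, again keeping the 6-week and steroid-taper criteria.
- Let the clinical team decide which exemptions to keep (Grade 4 endocrinopathy, Grade 4 asymptomatic amylase or lipase, recovering Grade 3 nephritis, steroid-responsive Grade 3 liver tests). Write each retained one identically in both texts and delete the rest.
- Reword the liver and colitis bullet so that the reach of the non-response qualifier is clear.

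The cost is amendment wording, with no added patients or procedures. The downside is that a few patients may stop treatment earlier than Table 3 alone would have required.
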